7.2.5 Sponsor Responsibility for Reporting Adverse Events

All Adverse Events will be reported to regulatory authorities, IRB/IECs and investigators in accordance with all applicable global laws and regulations.

8.0 STATISTICAL ANALYSIS PLAN

8.1 Statistical Analysis Plan Summary

8.1.1 Statistical Methods

8.1.1.1 Study Design

This is an open-label, single-arm, Phase II safety and efficacy study of combination therapy with pembrolizumab and olaparib in patients with advanced cholangiocarcinoma who have progressed on or cannot tolerate frontline chemotherapy.

8.1.1.2 Endpoints

1. Definition of Primary Endpoint

- a. Efficacy endpoint: overall response rate (ORR): defined as the proportion of subjects who achieve the best response (CR and PR) determined by RECIST1.1.

2. Definition of Secondary Endpoints

- a. PFS: defined as time from registration till the patient's disease progression or death from any cause whichever occurs first (those for whom event of progression or death not observed will be censored).
- b. OS: defined as time from registration till the patient's death from any cause (patient who are still alive at the end of the study will be censored).
- c. Overall response rate: defined as the proportion of subjects who achieve the best response (CR and PR) determined by irRC.
- d. To assess duration of response (DOR) of patients with advanced cholangiocarcinoma receiving a combination of pembrolizumab and olaparib.
- e. Safety endpoint: patients' toxicity profile, adverse event, serious adverse event, serious adverse even leading to discontinuation of the treatment, death. Safety and tolerability of the combination of olaparib and pembrolizumab is assessed by CTCAE v4.

A Phase II, Single-arm Study of Combination Pembrolizumab and Olaparib in the Treatment of Patients with Advanced Cholangiocarcinoma

Version 2.1: 17Mar2023

3 Definition of Exploratory Endpoints

- a. To correlate the baseline density of CD3 and CD8 in the tumor interior and invasive margin of the tumor, the expression of PD-L1, and the clonality of the T-cell repertoire with ORR, DOR, PFS, and OS.
- b. To correlate the difference between the baseline density of CD3 and CD8 in the tumor interior and invasive margin of the tumor, the expression of PD-L1, and the clonality of the T-cell repertoire and the same assessments after three weeks of treatment with ORR, DOR, PFS, and OS.
- c. To compare the density of CD3 and CD8 in the tumor interior and invasive margin of the tumor, the expression of PD-L1, and the clonality of the T-cell repertoire at three time points: at the time of disease progression, after three weeks of treatment, and at baseline.
- d. To correlate in the cholangiocarcinoma tissue the baseline expression of ERCC (DRCC+/-) or the baseline mutation status of IDH1 or 2 (mutant or non-mutant) with ORR, DOR, PFS, and OS.

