3.2 Secondary Objective(s) & Hypothesis(es)

(1) Objective:

1. Assess the duration of response (DOR) of patient receiving pembrolizumab and olaparib, taking best overall response to progression.
2. Assess progression free survival (PFS) of patients receiving pembrolizumab and olaparib taking best overall response to progression or death from any cause, whichever occurs first.
3. Assess overall survival (OS) of patients receiving pembrolizumab and olaparib from baseline to date of death or last follow up.
4. Assess the safety and tolerability of combined pembrolizumab and olaparib therapy.

(2) Hypothesis:

We propose that a PFS of 24 weeks and an OS of 40 weeks is clinically meaningful in patients who receive the combination of pembrolizumab and olaparib following failure on frontline therapy (due to cancer progression or intolerance of treatment).

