4.5.2 Secondary Endpoints

The secondary study endpoints are the duration of response (DOR), progression free survival (PFS), and overall survival (OS) in patients receiving the combination therapy. All of these endpoints are part of the clinical response assessment.

Primary Endpoint Definition

1. The objective response rate (ORR) is the proportion of all subjects with confirmed PR or CR according to RECIST 1.1, from the start of treatment until disease progression/recurrence (taken as reference for progressive disease, the smallest measurements recorded since the start of treatment).

Secondary Endpoint Definition

1. PFS is defined as the duration from the date of registration until disease progression (as defined above; using RECIST 1.1) or death occurs. Subjects who have not progressed will be right-censored at the date of the last disease evaluation.
2. OS is defined as the time of registration until death as a result of any cause.
3. Overall response rate (ORR) is defined as the sum of complete response (CR) + confirmed partial response (PR) and will be determined using the immune-related response criteria (iRECIST).
4. Grade 3 and 4 toxicities as defined by the NCI Common Terminology Criteria for Adverse Events (NCI CTCAE) v4.

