7.1.1.5.3 Subsequent Anti-Cancer Therapy Status

The investigator or qualified designee will review all new anti-neoplastic therapy initiated after the last dose of trial treatment. If a participant initiates a new anti-cancer therapy within 30 days after the last dose of trial treatment, the 30 day Safety Follow-up visit must occur before the first dose of the new therapy. Once new anti-cancer therapy has been initiated the participant will move into survival follow-up.

A Phase II, Single-arm Study of Combination Pembrolizumab and Olaparib in the Treatment of Patients with Advanced Cholangiocarcinoma

Version 2.1: 17Mar2023

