7.1.2.6.3 End of Treatment and Follow-up Tumor Imaging

In participants who discontinue study treatment, tumor imaging should be performed at the time of treatment discontinuation (± 4 week window). If previous imaging was obtained within 4 weeks prior to the date of discontinuation, then imaging at treatment discontinuation is not mandatory. In participants who discontinue study treatment due to the documented disease progression and the Investigator elects not to implement iRECIST, this is the final required tumor imaging.

In participants who discontinue study treatment without documented disease progression, every effort should be made to continue monitoring their disease status by tumor imaging using the same imaging schedule used while on treatment (every nine weeks in Year 1 or every twelve weeks after Year 1) to monitor disease status until the start of a new anticancer treatment, disease progression, pregnancy, death, withdrawal of consent, or the end of the study, whichever occurs first.

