7.1.5.3 Survival Follow-up

Participants who experience confirmed disease progression or start a new anticancer therapy, will move into the Survival Follow-Up Phase and should be contacted by telephone every 12 weeks to assess for survival status until death, withdrawal of consent, or the end of the trial, whichever occurs first.

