8.2.2 Analysis Plans for Secondary Objectives

Progression free survival (PFS) and overall survival (OS) will be evaluated using the methods of Kaplan and Meier (1958). 95% confidence interval will be constructed for the estimated median PFS and OS. The exploratory overall response rate will be estimated with its 95% exact confidence interval.

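### PFS counts a death at any time after scans stop but censors survivors at their last scan, and no sensitivity analysis shows how far the 24-week reading depends on this

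*Combined protocol and SAP*

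**What the plan says.** Section 8.1.1.2, item 2a, gives PFS as "defined as time from registration till the patient's disease progression or death from any cause whichever occurs first" and adds in parentheses that "those for whom event of progression or death not observed will be censored". It sets no limit on the gap between last scan and death, and no censoring date. The date is in section 4.5.2: "Subjects who have not progressed will be right-censored at the date of the last disease evaluation".

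Three sections decide who can die unscanned:

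- Section 7.1.2.6.3 asks for imaging to go on after treatment stops without progression, "to monitor disease status until the start of a new anticancer treatment" or another listed end point.
- Section 7.1.1.5.3: "Once new anti-cancer therapy has been initiated the participant will move into survival follow-up".
- Under section 7.1.5.3 such a patient "should be contacted by telephone every 12 weeks to assess for survival status until death". Withdrawal of consent and the end of the trial also end the calls.

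For the analysis, section 8.2.2 names Kaplan-Meier and says: "95% confidence interval will be constructed for the estimated median PFS and OS". Sections 4.5.2, 8.1.1.2 and 8.2.2 contain no rule for new anticancer therapy, none for death after missed scans, and no PFS sensitivity analysis. Section 3.2 sets the yardstick: "We propose that a PFS of 24 weeks and an OS of 40 weeks is clinically meaningful".

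**The concern.** Take a patient whose last scan, at week 12, is clean and who then starts another therapy. If the patient dies at week 50, PFS is an event at week 50, and 50 − 12 = 38 unscanned weeks count as progression-free. If the same patient is alive at the analysis, PFS is censored at week 12. Time at risk therefore depends on what happens later, which Kaplan-Meier does not allow for. The patients kept at risk past week 24 are those who went on to die, and some of them probably progressed unseen before then.

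The trial has one arm, so no control group shares the distortion. Section 2.1 expects PFS to be longer than with cytotoxic chemotherapy, and section 3.2 names 24 weeks as clinically meaningful. A reader of the planned output could not tell how much of the curve near week 24 rests on unscanned time.

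**Working it through.** The plan gives no PFS event count, power or precision, so there is no PFS figure to reproduce. The check is by simulation.

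**Inputs from the documents.** Scans every 6 weeks to week 24, then every 9, then every 12 (7.1.2.6.2); 36 months to complete follow-up (5.1); 36 patients (8.1.1.3); benchmarks of PFS 24 and OS 40 weeks (3.2).

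**Assumptions.** The share leaving scanning before progression is not in the documents; 10%, 20% and 30% were tried. Times are exponential. Accrual over 24 months with a 36-month cut-off gives 52 to 156 weeks of follow-up.

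**Scale.** One patient who is counted as progression-free at week 24, instead of as progressed, is worth 1/36 = 2.8 points.

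**First model.** Median PFS is 20.7 weeks, so true 24-week PFS is 0.5^(24/20.7) = 0.45 (0.447 in the simulated data with full scanning). Median survival after progression is 16 weeks. Estimated 24-week PFS with 20% leaving:

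| When patients leave | Full scanning | As written | Deaths within two scan intervals only | All leavers censored at last scan | New therapy as event |
|---|---|---|---|---|---|
| Unrelated to prognosis | 0.447 | 0.470 | 0.436 | 0.439 | 0.364 |
| Any time before progression | 0.447 | 0.504 | 0.476 | 0.488 | 0.396 |
| Last 40% of progression-free time | 0.447 | 0.507 | 0.493 | 0.510 | 0.428 |

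As written minus full scanning: 0.470 − 0.447 = +0.023, 0.504 − 0.447 = +0.057, and 0.507 − 0.447 = +0.060. Across leaving rates of 10%, 20% and 30%, the as-written estimate was 0.46–0.48, 0.47–0.51 and 0.48–0.54. With a true median of 24 weeks and 20% leaving, the Kaplan-Meier median rose from about 24 to about 28–33 weeks.

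**Second model.** This one was set to PFS 24 and OS 40 weeks, with 10% of PFS events being deaths without progression. As written minus full scanning at 24 weeks, 20% leaving:

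| Leavers | 36-month cut-off | 40-week cut-off |
|---|---|---|
| Unrelated to prognosis | +1.9 points | −1.2 points |
| Leaving because of deterioration | +6.2 points | 0.459 − 0.423 = +3.6 points |
| Better prognosis | 0.515 − 0.514 = +0.1 point | 0.484 − 0.508 = −2.4 points |

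At a 78-week cut-off with unrelated leaving, this model gave about zero; a separate run with fixed 78-week follow-up still gave an upward shift.

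**Why the sign can change.** Crediting unscanned time to leavers who die pushes the curve up. Removing leavers who survive, while keeping those who die as events, pushes it down. With long follow-up most leavers have died and the first effect usually wins; with short follow-up or better-prognosis leavers it need not.

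**The case against.** Much of the case against stands.

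- **Few patients may be affected.** Footnotes 5 and 11 of the flow chart in section 6.1 ask for imaging or reports until progression where possible. Sections 7.1.2.6.3 and 7.1.5.2 continue scans after treatment stops. What remains is mainly patients who start new therapy without documented progression.
- **The consequence is limited.** Nothing is tested against 24 weeks. With 36 patients the 95% half-width at 24 weeks is about 1.96 × √(0.447 × 0.553/36) = 0.16, well above a shift of 0.02 to 0.06. A bias does not average out as sampling error does, but it would not decide this trial.
- **The 16-week post-progression median is 40 − 24, and medians do not subtract.** For independent exponentials with medians 24 and 16, survival at week 48 is 3 × 0.25 − 2 × 0.125 = 0.50, so median OS would be 48, not 40. The second model is set to OS 40 and gives the same range, so the size does not hang on this.
- **The two-interval rule is not a clean replacement.** It was closer to the truth than the current text in all 27 combinations tried of leaving rate, leaving pattern and post-progression median (10, 16 or 24 weeks). None of those had better-prognosis leavers or short follow-up. In a setting of that kind it gave 0.38 against a true 0.447, where the current text gave 0.45.
- **The interval is not defined off treatment.** Within the first year section 7.1.2.6.3 has nine-weekly scans and section 7.1.5.2 six-weekly, while section 7.1.2.6.2 sends confirmed responders to twelve-weekly. Two intervals could mean 12, 18 or 24 weeks.

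A reader might also infer that everyone who leaves scanning is credited with unobserved time. Only those who later die are.

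**Conclusion.** The asymmetry is in the text, the route to it is in the follow-up sections, and no rule or sensitivity analysis deals with it. At the planned 36-month maturity the usual effect is upward: about +2 points if leaving is unrelated to prognosis and about +6 if it is tied to coming progression, at an assumed 20% leaving.

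Two stronger readings are tempting, and the documents do not support them. One is that PFS will be overstated. The documents give neither the number of leavers nor their prognosis, and the shift is nil or negative under some plausible conditions. The other is that two alternative analyses would bracket the true value. With leaving unrelated to prognosis, the two-interval rule (0.436) and new therapy as an event (0.364) both lie below the true 0.447.

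This is therefore a low-cost improvement to a descriptive secondary endpoint. The case for acting is that the planned output hides how much the 24-week reading depends on unscanned time.

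**What to change.** In section 8.1.1.2 item 2a, section 4.5.2 and section 8.2.2:

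1. Keep the current PFS definition as one analysis, and state the censoring date in 8.1.1.2 as well as in 4.5.2.
2. Pre-specify a sensitivity curve in which starting new anticancer therapy before documented progression is an event on that date.
3. Pre-specify a second curve in which a death counts only if it falls within two scheduled scan intervals of the last adequate scan; otherwise the patient is censored at that scan. Fix the interval in weeks once the scan schedules in sections 7.1.2.6.2, 7.1.2.6.3 and 7.1.5.2 have been reconciled.
4. Report the number of patients who left scanning before progression.
5. Call a PFS above 24 weeks robust only if the analyses agree, and describe them as showing the range.

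Section 3.2 measures PFS from best overall response, while 4.5.2 and 8.1.1.2 start at registration. The same edit should align these, so that the 24 weeks has one meaning.

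The cost is SAP wording, two extra Kaplan-Meier curves and a wider reported range. The dates needed are already due to be collected, and OS is unaffected.

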8.1.1.3 Sample Size and Accrual

The primary objective of the study is to assess the ORR of patients with advanced cholangiocarcinoma receiving a combination of pembrolizumab and olaparib. It is hypothesized that the combination of olaparib and pembrolizumab will improve the overall response rate (ORR) from 17.5% (historical control) to 35% in patients with advanced cholangiocarcinoma. The sample size is based on the number of patients that are anticipated to complete the primary objective.

Simon's two-stage Optimum design will be used to test the null hypothesis of $P \leq 0.05$ versus the alternative hypothesis of $P \geq 0.25$. At the first stage, 13 patients will be treated with the combination of olaparib and pembrolizumab. The trial will be terminated if 2 or fewer patients respond. If there are more than 2 responses, the trial will go on to the second stage and 20 more patients will be enrolled to a total of 33 patients. If the total number responding among the 33 patients is ≤ 8 , the null hypothesis will not be rejected and the combination of olaparib plus pembrolizumab will not be investigated further. Using this statistical method, there is a 0.092 (9.2%) probability of erroneously concluding that this drug combination is effective when it actually is not (targeted value of 0.1). If the drug is actually effective, there is a 0.192 probability of concluding that it is not (targeted value of 0.2). The power of the design is 85% with a one-sided significance level of 0.05. If we assume a 10% patient dropout rate, then a total of 36 patients will be needed for the trial.

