2.0 TRIAL DESIGN

2.1 Trial Design

We propose an open label, one-arm study to assess the safety and efficacy of olaparib and pembrolizumab in patients with cholangiocarcinoma who have progressed on or cannot tolerate gemcitabine-based therapy.

The primary objective of the study is to assess the ORR of patients with advanced cholangiocarcinoma receiving a combination of pembrolizumab and olaparib. It is hypothesized that the addition of olaparib will improve the response rate of second line systemic therapy from 17.5% to 35% in patients with advanced cholangiocarcinoma.

The study is designed to enroll 33 subjects (for 85% power) with advanced stage cholangiocarcinoma to test the hypothesis that the combination of olaparib and pembrolizumab will increase the ORR in comparison with the ORR from second line systemic chemotherapy (historical control) in this patient population. As our primary study endpoint, which is also being used to determine the sample size of the study, we propose that the combination of olaparib and pembrolizumab will increase the ORR to 35% from 17.5% (achieved with systemic cytotoxic chemotherapy including mFOLFOX—historical control). To allow a 10% patient drop off rate, we expect to enroll a total of 36 subjects into this study. In addition, as secondary study endpoints we expect to see an increase in the PFS and OS of patients receiving combination therapy compared to cytotoxic chemotherapy.

[figure not shown]
A Phase II, Single-arm Study of Combination Pembrolizumab and Olaparib in the Treatment of Patients with Advanced Cholangiocarcinoma
Version 2.1: 17Mar2023

In this study, we propose the collection of three biopsies—one at baseline prior to the start of treatment, one at the beginning of week 4, three weeks after the administration of combination olaparib and pembrolizumab, and one at the time of cancer progression—for the elucidation of exploratory study endpoints. Patients will have a CT or MRI scan at the beginning of treatment and then every 6 weeks thereafter for the first six months of study treatment administration, then every 9 weeks for up to 12 months after the start of treatment, followed by every 12 weeks up to 24 months on study. All patients will continue to receive olaparib and pembrolizumab combination treatment as tolerated unless unacceptable toxicities or cancer progression occur, at which time therapy will cease. In the absence of any problems, the planned study duration is 20-36 months.

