3.0 OBJECTIVE(S) & HYPOTHESIS(ES)

3.1 Primary Objective(s) & Hypothesis(es)

(1) Objective:

Assess the objective response rate (ORR) of patients receiving pembrolizumab and olaparib combination therapy.

(2) Hypothesis:

The combination of olaparib and pembrolizumab regimen will improve the response rate of second line systemic therapy from 17.5% to 35% in patients with advanced cholangiocarcinoma, based on RECIST1.1.

A Phase II, Single-arm Study of Combination Pembrolizumab and Olaparib in the Treatment of Patients with Advanced Cholangiocarcinoma
Version 2.1: 17Mar2023

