4.4 Overall Rationale

4.4.1 Rationale for the combination of olaparib with pembrolizumab:

Studies reveal a direct causal relationship between cancer and immune dysfunction, whereby tumor cells and their microenvironment are able to evade immune attack by exploiting various immunoregulatory mechanisms in a process termed cancer immunoediting [21]. Regulatory pathways that limit the immune response to cancer are becoming increasingly well characterized and provide new strategies in cancer therapy. Monoclonal antibodies targeting PD-1 that boost the immune system are being developed for the treatment of a number of cancers. On September 4, 2014, the U.S. Food and Drug Administration granted accelerated approval to pembrolizumab (KeytrudaTM, Merck Sharp & Dohme Corp.) for the treatment of patients with unresectable or metastatic melanoma [22]. In May of 2017, the FDA approved pembrolizumab for use in patients who fit these disease criteria and are microsatellite instability-high (MSI-H) or mismatch repair deficient (dMMR). Pembrolizumab is a monoclonal antibody that binds to the PD-1 receptor and blocks its interaction with ligands PD-L1 and PD-L2, thereby releasing PD-1 pathway-mediated inhibition of the immune response, including anti-tumor immune response. The response rate of pembrolizumab in patients with advanced cholangiocarcinoma was 17% in a phase I study [23].

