4.5 Rationale for Endpoints

After first-line treatment with a gemcitabine-based regimen, there is no recommended, standard second-line chemotherapy for patients with metastatic gallbladder cancer and cholangiocarcinoma. A multicenter survey and pooled analysis with published data showed that response rates (RRs) to second-line chemotherapy were low (3.4 %), with median PFS and OS of 3.0 months and 6.6 months, respectively [8]. Immune checkpoint inhibitors have shown durable disease control in multiple types of cancer, e.g., melanoma, renal cell carcinoma, non-small cell lung cancer, etc. We propose that an improvement in overall response rate of 35% in patients who receive the combination of pembrolizumab and olaparib after cancer progression or intolerance to frontline treatment (compared to a response rate of 17.5% in patients who received second line systemic chemotherapy per historical control) will be considered clinically meaningful.

A Phase II, Single-arm Study of Combination Pembrolizumab and Olaparib in the Treatment of Patients with Advanced Cholangiocarcinoma

Version 2.1: 17Mar2023

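### Section 8.1.1.3 prints hypotheses (5% vs 25%) and operating characteristics (85% power, one-sided 0.05) that its Simon boundaries do not have; for 17.5% vs 35% the rule gives 80.8% power and 9.2% type I error

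*Combined protocol and SAP*

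**What the plan says.** Section 8.1.1.3 opens with an improvement in ORR from 17.5% to 35%. Its next paragraph says that a Simon two-stage "Optimum design will be used to test the null hypothesis of" P ≤ 0.05, against P ≥ 0.25. The rule is:

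- Stage 1 has 13 patients; the trial stops if 2 or fewer respond.
- Stage 2 adds 20, for 33 in all; the null is not rejected if 8 or fewer respond, so success needs at least 9.

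The paragraph then gives two sets of operating characteristics for this one rule. The first says "there is a 0.092 (9.2%) probability of erroneously concluding that this drug combination is effective when it actually is not (targeted value of 0.1"), and puts the probability of missing an effective regimen at 0.192 (target 0.2). The second follows at once: "The power of the design is 85% with a one-sided significance level of 0.05".

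Section 2.1 repeats the second set: "The study is designed to enroll 33 subjects (for 85% power) with advanced stage cholangiocarcinoma". On the hypotheses, sections 2.1, 3.1 and 4.5 agree with the opening of 8.1.1.3; section 3.1 says that the regimen "will improve the response rate of second line systemic therapy from 17.5% to 35% in patients with advanced cholangiocarcinoma". The 5% and 25% rates appear only in that one sentence of 8.1.1.3.

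**The concern.** One decision rule is given two null/alternative pairs, two type I error rates and two power figures. A type II error of 0.192 means power of 0.808, not 0.85. A 0.092 chance of a false positive is not a 0.05-level test. These conflicts show on the page before anything is calculated.

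This is the trial's only pre-specified efficacy decision rule, and it settles whether the combination is pursued. A reader who takes the one-sided 0.05 at face value would treat 9 of 33 as significant at 5%. A reader who takes the printed null at face value would think that success means having excluded 5%, when the objective is to exceed 17.5%.

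**Working it through.** **Inputs (section 8.1.1.3):** n1 = 13, r1 = 2, n2 = 20, n = 33, r = 8. Rates: 17.5% and 35% (2.1, 3.1, 4.5 and the opening of 8.1.1.3); 5% and 25% (the Simon sentence).

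**Formula.** With true response rate p, X1 ~ Bin(13, p) and X2 ~ Bin(20, p),

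P(declare effective) = Σ over x = 3,…,13 of P(X1 = x) × P(X2 ≥ 9 − x).

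**Step 1: reproduce the quoted 0.092 and 0.192, using 17.5% and 35%.** Each product is P(X1 = x) × P(X2 ≥ 9 − x):

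| x | product at p = 0.175 | product at p = 0.35 |
|---|---|---|
| 3 | 0.2239 × 0.1223 = 0.0274 | 0.1651 × 0.7546 = 0.1246 |
| 4 | 0.1187 × 0.2644 = 0.0314 | 0.2222 × 0.8818 = 0.1960 |
| 5 | 0.0453 × 0.4736 = 0.0215 | 0.2154 × 0.9556 = 0.2058 |
| 6 | 0.0128 × 0.7058 = 0.0090 | 0.1546 × 0.9879 = 0.1528 |
| 7 | 0.0027 × 0.8882 = 0.0024 | 0.0833 × 0.9979 = 0.0831 |
| 8 to 13 | 0.0005 | 0.0462 |
| **Sum (unrounded terms)** | **0.0922** | **0.8084** |

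Type I error is 0.0922 and type II error is 1 − 0.8084 = 0.1916. Both match the quoted 0.092 and 0.192.

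**Step 2: identify the design.** An exhaustive search for the Simon optimal design with p0 = 0.175, p1 = 0.35, type I error at most 0.10 and power at least 0.80 returns exactly 2/13, 8/33, with expected sample size 21.1 under the null. For 5% against 25% at the same targets, the optimal design is 0/6, 2/23. At 0.05 and 85% power it is 0/8, 3/26.

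**Step 3: the rule under the printed hypotheses.**

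| True rate | P(declare effective) | P(stop at stage 1) |
|---|---|---|
| 5% | 0.00002 | 0.975 |
| 25% | 0.391 | 0.333 |

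At a true rate of 25% the rule would miss the effect 61% of the time (1 − 0.391).

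**Step 4: can 33 patients give 85% power at one-sided 0.05 for 17.5% against 35%?**

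| Version | Type I error | Power |
|---|---|---|
| Two-stage as planned, ≥9 of 33 | 0.092 | 0.808 |
| Two-stage with the 2/13 stop kept and binding, ≥10 of 33 | 0.0455 | 0.730 |
| Single stage, ≥9 of 33 | 0.109 | 0.868 |
| Single stage, ≥10 of 33 | 0.0508 | 0.770 |
| Normal approximation, n = 33 | 0.05 | 0.787 |
| Arcsine approximation, n = 33 | 0.05 | 0.748 |

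None does. The smallest exact single-stage design that does has 46 patients (≥13 responders: type I error 0.048, power 0.868). The Simon minimax design also needs 46 (3/20, 12/46: 0.0454 and 0.851), and the optimal design needs 57 (4/20, 14/57: 0.0463 and 0.850).

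**The case against.** The true error rates are not hidden: 0.092 and 0.192 stand directly before the wrong sentence, and the boundaries can be applied as printed. Section 8.2.1 plans no p-value, only the ORR with an exact 95% interval. For 9 of 33 that interval is about 13.3% to 45.5% and includes 17.5%, so the planned report would not itself present 9 of 33 as significant at 5%. This stands, and it limits the practical harm. It does not remove the contradiction: the null, the alternative, the level and the power each still carry two values.

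A second argument is that 85% appears twice (2.1 and 8.1.1.3) and 0.192 once, so the sponsor may have intended 85% power at 0.05. The boundaries answer this. They are the optimal design for targets of 0.10 and 0.20, which are the targets the paragraph names, and no version with 33 patients reaches 85% at 0.05. If the sponsor did want those characteristics, the sample size would have to change, not only the wording.

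The low power at 25% would be a real loss only if 25% were the target. It is not, since every other section says 35%. The figure shows that the printed hypotheses cannot belong to this rule.

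**Conclusion.** The concern holds. The boundaries, the sample size and the quoted 0.092 and 0.192 form one coherent design for 17.5% against 35%. The printed 5% against 25% and the claim of 85% power at one-sided 0.05 are wrong for it. Type I error is 0.092 against the claimed 0.05, nearly double. Power is 0.808 against 0.85, a shortfall of 4.2 points. These figures assume independent binomial responses, a binding stop after 13 patients and exactly 33 patients in the final count.

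A side point, which would not carry the finding alone: the plan labels 17.5% as second-line chemotherapy, yet section 4.5 reports that "response rates (RRs) to second-line chemotherapy were low (3.4" %). Section 4.4.1 says: "The response rate of pembrolizumab in patients with advanced cholangiocarcinoma was 17% in a phase I study". The null of 17.5% lies above both figures, but the plan should say which comparison it represents, because that governs how a positive result is read.

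**What to change.** In section 8.1.1.3:

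- Change the tested hypotheses to P ≤ 0.175 against P ≥ 0.35.
- Delete the sentence claiming 85% power at one-sided 0.05. State instead: one-sided type I error 0.092 (target 0.10) and power 0.808 (target 0.80).
- Keep the stage sizes of 13 and 33 and both boundaries.

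In section 2.1, remove the 85% power claim or replace it with 80.8%. In 2.1 and 4.5, name the source of the 17.5% and reconcile it with the 3.4% and 17% cited elsewhere.

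The cost is wording in a few sentences, with no extra patients and no change to conduct; the stated level and power become less favourable. If the sponsor confirms that 85% power at one-sided 0.05 was the requirement, rewording will not do, and the design must be recalculated with at least 46 evaluable patients.
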